Treatment Plan	Each Subject will receive one standard study hemodialysis treatment with heparin anticoagulation during which all procedures noted in Appendix 1 will be performed. Subsequently each subject will receive hemodialysis with the added SCD filter anticoagulated with regional citrate.
Data Safety Monitoring	This is a small feasibility study. A safety analysis will be performed on each patient prior to their next hemodialysis treatment by the PI.
Key Measurements	
 ❖ Adverse events ❖ Regional wall abnormalities and myocardial strain on Echocardiogram
Exploratory Measurements	
 ❖ Soluble Markers (Elastase, Hs CRP, IL-6, IL-10, IL-17, IL-23, G-CSF, TNF-α, MCP-1, L-selectin, neopterin, IL-1β, IL-8) ❖ Leukocyte flow cytometry (circulatory monocyte subsets and circulatory activated neutrophils) ❖ WBC and platelet counts

Primary Analyses	Descriptive analysis will be conducted on the following parameters in all Subjects exposed to any study hemodialysis treatment: 
 ❖ Adverse events ❖ Regional wall abnormalities and myocardial strain ❖ Clinical laboratory and physiological measurements
Secondary Analyses	A number of secondary analyses will be conducted, including the following: 
 ❖ Mean change from baseline in cytokines at the end of each treatment ❖ Mean change from baseline in markers of inflammation at the end each treatment
Study Periods and Study Duration	
 ❖ The total duration of participation will be approximately 3 weeks.

1. Background and Rationale

More than 400,000 people are currently treated by hemodialysis (HD) in the US end stage renal disease (ESRD) program. The mortality in this group of patients is unacceptably high with almost half of the deaths due to cardiovascular disease (CVD). Strategies to reduce the mortality of HD patients with directed interventions at cardiovascular risk factors have largely been ineffective. It is well recognized that HD patients suffer excess morbidity and mortality, mainly due to cardiac failure and sudden death rather than traditional thrombotic occlusion leading to acute myocardial infarction (AMI).^{1,2} The excess cardiovascular risk is not the result of the traditional factors associated with CVD but a combination of non-traditional factors unique to chronic kidney disease (CKD).

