Assessment: Echocardiographic parameters which are less (but not entirely) preload and afterload dependent include quantitation of regional wall motion abnormalities as well as calculation of GLS. Normative values for regional wall motion abnormalities are defined as normal thickening and endocardial excursion in all regions and any deviation from normal thickening or excursion is considered abnormal. Regional wall motion will be scored using a standard wall motion scoring scheme. (1=normal; 2=hypokinetic; 3= akinetic; 4=dyskinetic). Scores will be tabulated for each of 16 predefined segments and a global wall motion score calculated as the sum of individual scores divided by the number visualized segments. For this scheme a score of 1 represents normal ventricular function with progressively higher numbers representing progressively worse systolic function. Scores from pre HD, post HD and 24 hour post HD Echos from all 10 patients will be collated and analyzed for statistical significance between Treatment 1 and Treatment 2 groups.

Global longitudinal strain will be obtained using tissue tracking methodology³⁸. There is a significant range within the left ventricle of normal values for regional strain depending on wall location. Values for normal GLS in normal controls have ranged from -16.0 to -22.0. Patients with systemic diseases including hypertension, diabetes and renal disease have all been described to have reduced GLS in the absence of overt systolic dysfunction. As “normal” values for GLS cannot be predicted in the patient population under consideration each patient will serve as his or her own control for tracking improvement or deterioration in global longitudinal strain.

Assessment: The largest body of data regarding using global longitudinal strain for tracking myocardial performance is in the patients receiving cardiotoxic chemotherapeutic agents where a threshold of 10-15% change has been considered as significant variation from baseline³⁹. This will be used as a dichotomous threshold for defining either improvement or deterioration in GLS.

Echocardiographic images will be interpreted at the Echo Laboratory, Frankel Cardiovascular Center, Floor 3. Area B, University of Michigan, Ann Arbor, MI

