8.5 Study Exit Procedures

A Study Termination form will be completed for all patients who have completed the Study Procedures according to the protocol as well as for those who are terminating early for any cause

9. Statistical Considerations

Sample size determination for primary outcome regional wall abnormalities: Our consultant, [name] has previously demonstrated a difference in this variable in 8 to 10 patients using a similar protocol to this proposal when comparing standard and biofeedback dialysis and dialysis cooling ^{33,34}. Sample size of 10 would appear to be sufficient to detect a difference of 20% and is based upon a standard deviation of 14%, significance level of 0.05 and 80% power. In the [name] studies, differences of greater than 20% were observed. We plan to recruit 10 patients in this study, to better ensure an adequate sample size to obtain statistically relevant primary and secondary endpoint comparisons. The patients will serve as their own controls, comparing BL-SHH parameters to SCD therapy parameters. Independent t-test will be used to compare the peak frequency of MS between SHH and SCD sessions. Global LVEF and wall motion in 16 segments in 8 regions at each time point in the dialysis session will be compared using repeated measures and Bonferroni's test for multiple comparisons. IDWG will be compared using paired and unpaired non-parametric testing or t-test if the variable is

normally distributed. These approaches have shown significance in prior studies for MS in HD. Statistical correlations are planned for regional wall abnormalities, inflammatory indices, monocyte subsets and pre-dialysis blood pressures ^{33,34}

10. Adverse Events

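### The primary analysis is descriptive in the synopsis but a powered test in Section 9, and the 80% power is tied to no defined endpoint

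*Combined protocol and SAP*

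**What the plan says.** - **Synopsis, Primary Analyses.** "Descriptive analysis will be conducted on the following parameters in all Subjects exposed to any study hemodialysis treatment". The parameters are adverse events, regional wall abnormalities with myocardial strain, and clinical laboratory and physiological measurements. None is singled out.
- **Section 9, sample size.** It opens with "Sample size determination for primary outcome regional wall abnormalities" and justifies ten patients by "a difference of 20% and is based upon a standard deviation of 14" percent, with "significance level of 0.05 and 80% power". It does not say what the percentages are percentages of, or whether the SD is per session or of within-patient differences.
- **Section 9, analyses.** It gives an independent t-test of *peak frequency of MS* between the heparin (SHH) and SCD sessions. It also gives repeated measures with Bonferroni for LVEF and for wall motion in 16 segments. The same paragraph says that each patient is his or her own control.
- **Section 8.4.1.** Segments are scored from 1 (normal) to 4 (dyskinetic) and averaged over the segments visualized. The pre, post and 24-hour scores are to be "analyzed for statistical significance between Treatment 1 and Treatment 2 groups", with no test named. Strain gets a 10-15% change threshold for improvement or deterioration, but no significance test.
- **Echo schedule (8.3.1.1, 8.3.1.38, 8.3.1.40 and Appendix 1).** Echoes are done before, after and 24 hours after each treatment.
- **Definition of stunning (Section 1).** It is conceptual only: a transient, ischemia-mediated fall in myocardial function. There is no echo threshold and no counting rule.

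**The concern.** A primary analysis cannot be both descriptive over three groups of parameters and a powered test of one outcome. The plan gives no order of precedence. Once the data are in, stunning frequency, the wall motion score or segmental wall motion could each be presented as the primary result, at the post-dialysis or the 24-hour echo.

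The one test that Section 9 names for stunning cannot be run as written, because its input is neither defined nor measured. It also treats two sessions in the same patient as two separate groups. A reader told that the trial had 80% power would not know for which measure.

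**Working it through.** **1. The statements side by side**

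| Place | Nature | Measure | Test |
|---|---|---|---|
| Synopsis | Descriptive | Three parameter groups | None |
| Section 9, sample size | Powered | Regional wall abnormalities, unit not given | Not named |
| Section 9, analysis | Inferential | Peak frequency of MS, undefined | Independent t-test |
| Section 9, analysis | Inferential | LVEF and 16-segment wall motion | Repeated measures, Bonferroni |
| Section 8.4.1 | Inferential | Wall motion score, 1 to 4, three time points | Not named |

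A peak within a session needs images during the session. No echo is scheduled between the pre-dialysis and post-dialysis ones.

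**2. The plan's own figure**

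Inputs from Section 9: difference 20, SD 14, alpha 0.05, power 80%. Assumptions: two-sided test, and a percentage-scale endpoint.

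Independent samples, normal approximation:
n = 2 × (1.960 + 0.842)² × (14/20)² = 2 × 7.85 × 0.49 = 7.7, so 8 per session.

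With the exact noncentral t, 9 per session are needed (power 81.2%), and 10 give 85.5%. The stated ten is therefore consistent with the inputs.

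**3. The same inputs in the paired design**

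If 14 is the SD of within-patient differences, 7 patients suffice (88.0%; 6 give 79.7%). Ten give 97.9%, and the difference detectable with 80% power is 13.9 points.

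If 14 is the per-session SD, the SD of differences is 14 × √(2(1 − ρ)), where ρ is the within-patient correlation. The documents give no ρ, so a range is shown. The last two columns apply the planned independent t-test to paired data (simulation, 200,000 repetitions, 10 patients, normal data).

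| Assumed ρ | SD of differences | Paired test: power for 20 points | Independent test: actual type I error | Independent test: power for 20 points |
|---|---|---|---|---|
| 0 | 19.8 | 81.1% | 5.0% | 85.5% |
| 0.3 | 16.6 | 92.3% | 2.2% | 89.1% |
| 0.5 | 14.0 | 97.9% | 1.0% | 92.0% |
| 0.7 | 10.8 | 99.9% | 0.2% | 94.8% |

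With positive correlation the independent test is too conservative. It does not inflate false positives. From ρ = 0.3 upward it also has less power than the paired test.

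**4. Whether the 80% carries over to the other analyses**

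- *Wall motion score.* No difference or SD is given on the 1-to-4 scale, so no power can be computed.
- *Segmental analysis with Bonferroni.* The plan does not say how many comparisons are corrected for. As an illustration with 16, alpha is 0.05/16 = 0.003125. With the same inputs on a percentage scale, power at ten patients is then 44% (independent) or 68% (paired, SD of differences 14).
- *Descriptive analysis.* Power does not apply.

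**The case against.** Section 4.1 calls this an exploratory pilot and the synopsis calls it a small feasibility study, so a formal error rate matters less than in a confirmatory trial. Section 9 does name one primary outcome, and that outcome is also on the synopsis list. The inputs may come from the two dialysis studies that Section 9 cites, where the unit may be plain.

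Part of this stands. It limits the weight of the point, and it rules out three stronger readings that a reader might infer:

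- *That the 20% and 14% fit none of the analyses.* Not shown. Section 9 attaches them to regional wall abnormalities, and they support ten patients under the independent t-test if its endpoint is a percentage. What is missing is the unit and the type of SD.
- *That three measures tested at 0.05 give a false-positive risk of 1 − 0.95³ = 14%.* This would count strain as a third test, but neither Section 8.4.1 nor Section 9 names a significance test for strain. Independence is also implausible for measures taken from the same echocardiograms.
- *That ten patients are too few.* Ten suffice in every single-test, percentage-scale case above.

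The pilot label does not remove the conflict. The synopsis also calls the trial Phase II, Section 3 sets out to evaluate efficacy, and Section 9 invokes alpha and power. Having done so, the plan must say what they apply to.

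**Conclusion.** The point holds. The synopsis and Section 9 disagree on whether the primary analysis is descriptive or inferential, and Sections 9 and 8.4.1 together list three inferential analyses without naming one as primary. The t-test of peak frequency of MS cannot be computed from the scheduled echoes, and its independent form contradicts the within-patient design. The 80% power belongs to no defined endpoint.

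The number for the pairing error is a type I error of about 1% instead of 5%. It rests on an assumed correlation of 0.5, normal data and a two-sided test. The power figures assume a percentage-scale endpoint. The inconsistency itself rests on the text alone. No change in sample size is shown to be needed.

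**What to change.** Make the synopsis, Section 8.4.1 and Section 9 say the same thing:

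1. Name one primary efficacy measure built from the scheduled echo scores. One example is each patient's pre-to-post change in regional wall motion, taken either as the score already defined or as the share of visualized segments that worsen by at least one grade. The choice is the sponsor's.
2. Compare SCD with SHH by one within-patient (paired) test at 0.05, in place of the independent t-test. Drop peak frequency of MS, or define it from echoes that are scheduled.
3. State the unit of the 20% and 14% and which SD the 14% is. If that cannot be recovered, restate the power for the chosen measure.
4. Label LVEF, strain, 24-hour and laboratory comparisons as exploratory, and keep adverse events as descriptive safety.
5. Give a time window for the post-dialysis echo. Section 1 says that most stunned areas improve within 30 minutes after dialysis, and Section 8.3.1 lists this echo after the circuit has been disassembled, with no window.

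Items 1 to 4 cost protocol and SAP wording only, with no added patients or visits. The window in item 5 may constrain the timing of an echo that is already scheduled. The downside is that the other echo measures lose primary status.

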1. **Select the base Calcium-infusion Table 1 Rate at QB=200:** The amount of calcium removed from the circuit blood by the dialyzer is altered by the hemoglobin (Hb) and albumin level. The initial calcium infusion rate is prescribed by the PI based on the last laboratory hemoglobin and serum albumin using Table 1. At start the nurse adjusts the initial Ca-infusion Table 1 Rate using the Crit-Line online optical hemoglobin value and the last serum albumin and confirms any change with the PI. The systemic ionized calcium at 1 hour is charted but not used to alter the initial rate. An offset is always applied to the Table 1 Rate based on the hourly net ultrafiltration rate (see below).

Table 1 ACD-A (Citrate) Infusion Fixed Rate, Blood flow = 200 ml/min, ACD-A flow = 400 ml/hour

Rate in ml/hour of the Ca-infusion (20 gm CaCl₂ + 0.8 L 0.9% saline). The rate is defined by the systemic albumin and hemoglobin at a blood flow of 200 ml/min.

Hb	6-6.9 g/dL	7-7.9 g/dL	8-8.9 g/dL	9-9.9 g/dL	10-10.9 g/dL	11-11.9 g/dL	12-12.9 g/dL	13-13.9 g/dL	14-14.9 g/dL	15-15.9 g/dL
Albumin										
0.0-0.7 g/dL	110	106	102	98	93	90	86	82	78	73
0.8-1.2 g/dL	116	112	108	103	99	95	91	87	82	78
1.3-1.7 g/dL	122	118	113	109	105	100	96	91	87	82
1.8-2.2 g/dL	129	125	120	115	110	106	101	96	91	87
2.3-2.7 g/dL	136	131	126	121	116	111	106	101	96	91
2.8-3.2 g/dL	142	137	132	127	121	116	111	106	101	96
3.3-3.7 g/dL	149	143	138	132	127	121	116	111	105	100
3.8-4.2 g/dL	155	149	144	138	132	127	121	116	110	104
4.3-4.7 g/dL	162	156	150	144	138	132	126	120	115	108
4.8-5.2 g/dL	168	162	156	150	144	137	131	125	119	113

2. Adjust the base Ca-infusion Table I Rate at QB=200 using systemic hemoglobin changes The systemic hemoglobin (Hb) level in the arterial limb of the blood circuit will be continuously measured and displayed by an optical sensor (Crit-Line III).

The Hb level may decrease due to bleeding and increase due to blood transfusions or hemoconcentration due to excessive ultrafiltration. If the Hb increases, the circuit plasma flow will decrease and the dialyzer calcium losses will decrease, therefore the calcium infusion rate must be decreased. If the Hb decreases, the circuit plasma flow will increase and the dialyzer calcium losses will increase, therefore the calcium infusion rate must be increased.

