8.12 Exploratory Measurements

- ❖ Soluble Markers (Elastase, Hs CRP, IL-6, IL-10, TNF- α , L-Selectin, MCP-1, IL-17, IL-23, IL-8, G-CSF, IL-1 β , WBC, platelet count, Neopterin)
- ❖ Leukocyte flow cytometry (circulatory monocyte subsets)
- ❖ SCD integrity monitoring during treatment will include visual inspection for clotting and hemolysis, and additional testing following return of hemofilter to the research laboratory.

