- 8.3.1.23 At 1 hour, stop heparin, change dialysate to zero calcium and start citrate and calcium infusion. After 3 minutes of citrate and calcium infusion, stop the blood pump, clamp the venous return line. Please refer to Fresenius Operator's Manual on how to integrate the SCD to circuit. Within the first 10 minutes of initiating citrate with the integrated *SCD* obtain blood from sampling port of arterial segment of extracorporeal circuit (pre-citrate infusion) and send for iCa using a bedside i-STAT Analyzer (**Appendix 2**).

At 2 Hour Into Study Treatment (For SCD Treatment Only)

- 8.3.1.24 For *SCD treatment protocol*, obtain blood for iCa from extracorporeal blood circuit (pre-citrate infusion) arm using the bedside i-STAT Analyzer.

At 3 Hours Into Study Treatment (For SCD Treatment Only)

- 8.3.1.25 For *SCD treatment protocol*, obtain blood for iCa from extracorporeal blood circuit (pre-citrate infusion) using the bedside i-STAT Analyzer.

At 4 Hours Into Study Treatment (For SCD Treatment Only)

8.3.1.26 For *SCD treatment protocol*, obtain blood for iCa from extracorporeal blood circuit (pre-citrate infusion) using a bedside i-STAT Analyzer.

At 5 Hours Into Study Treatment (SHH and SCD Treatment except if indicated otherwise)

8.3.1.27 Obtain blood for basic metabolic panel according to instructions in **Appendix 2**.

8.3.1.28 Obtain blood for CBC with differential and platelets according to instructions in **Appendix 2**.

8.3.1.29 Obtain blood for systemic soluble markers according to instructions in **Appendix 2**.

8.3.1.30 Obtain blood for flow cytometry according to instructions in **Appendix 2**.

8.3.1.31 For *SCD treatment protocol*, obtain blood for iCa with i-STAT Analyzer.

End the Study Treatment Period

8.3.1.32 Discontinue heparin infusion in heparin anticoagulant treatment or citrate infusion in citrate anticoagulant treatment.

8.3.1.33 Remove any peripheral intravenous catheter(s).

8.3.1.34 For Subjects with AV fistula or graft, remove needles or venous cannula (i.e. angi catheters) and obtain hemostasis according to Investigator orders or per hospital routine.

8.3.1.35 For Subjects with tunneled catheters, disconnect tubing and instill heparin flush according to Investigator orders or per hospital routine.

8.3.1.36 Obtain oral temperature, BP, pulse, and weight without shoes or overclothes.

8.3.1.37 Disassemble the Study Circuit.

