8.4.2 Soluble Markers Assay Methods

Assays for soluble markers (Table 3) are either sandwich or competitive ELISAs' and will be performed according to manufacturer's suggested protocols. High sensitivity Quantikine kits from R&D Systems will be run with Quantikine® Immunoassay Control Group 10 Catalog Number: QC41 which provides high, medium and low reference for high sensitivity kits, including IL-1 β , IL-6, IL-8, IL-10 and TNF α . MCP-1 Quantikine kit will be run with Immunoassay Control Group 1 Catalog Number: QC01-1, which provides high, medium and low reference for a wide range of soluble markers including MCP-1. Inter assay controls are provided within the kits for CD62L, elastase, hsCRP, and neopterin. The 96 well format plates will be read using a Molecular Devices Spectramax M5 plate reader, and acquired data analyzed using SoftMax Pro 6.5.1 Software. Inter and Intra Assay precision will be calculated and criteria for acceptance established using expected values provided by the kit manufacturers. Non-compliant analysis will be repeated until criteria are met.

The slated soluble markers are expected to deviate from reported normal values with in patient populations with myocardial stunning. Baseline values will be compared to reported normal and diseased values as reported in the literature and where reported by kit manufacturers. Each patient's pre-treatment value will be used as its own baseline and this value compared to those obtained with the normal hemodialysis session and with SCD therapy. Statistical significance of assay values will be determined using Anova for repeated measures and paired student t test where appropriate.

Table 3. Assays for Soluble Markers

Soluble Marker	Assay Kit	Assay Type	Inter Assay Controls
Elastase	ThermoFisher BMS269	Sandwich ELISA	High/Low Included in Kit
Hs CRP	ALPCO 30-9710s	Sandwich ELISA	High/Low Included in Kit
IL-1 β	R&D Systems HSLB00D	Sandwich ELISA	R&D Systems QC41
IL-6	R&D Systems HS600B	Sandwich ELISA	R&D Systems QC41
IL-8	R&D Systems HS800	Sandwich ELISA	R&D Systems QC41

IL-10	R&D Systems HS100C	Sandwich ELISA	R&D Systems QC41
TNF α	R&D Systems HSTA00E	Sandwich ELISA	R&D Systems QC41
CD62L (L-Selectin)	Abcam	Sandwich ELISA	Single Control
MCP-1	R&D systems DCP00	Sandwich ELISA	R&D Systems QC01-1
Neopterin	TECAN IBL RE59321	Competitive ELISA	High/Low Included in Kit

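### Raw change from baseline to the end of dialysis is not corrected for hemoconcentration, so fluid removal alone can look like a rise in retained markers and cells, or hide a fall

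*Combined protocol and SAP*

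**What the plan says.** The Synopsis (Secondary Analyses) lists "Mean change from baseline in cytokines at the end of each treatment" and "Mean change from baseline in markers of inflammation at the end each treatment". Section 8.4.2 takes the value measured before treatment as the reference for each person: it "will be used as its own baseline and this value compared to those obtained with the normal hemodialysis session and with SCD therapy". It adds: "Statistical significance of assay values will be determined using Anova for repeated measures and paired student t test where appropriate". Section 8.12 places cell counts in the same list as the soluble markers ("WBC, platelet count, Neopterin").

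Samples are drawn before dialysis and again under the heading "At 5 Hours Into Study Treatment (SHH and SCD Treatment except if indicated otherwise" in Section 8.3.1. Section 4.1 gives both sessions a first hour without ultrafiltration, then 4 h of high ultrafiltration to reach dry weight.

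The protocol recognises the phenomenon. Section 6.3.4, step 2, says that hemoglobin may rise through "hemoconcentration due to excessive ultrafiltration", but uses this only to adjust the calcium infusion. No section normalises marker concentrations, white cells or platelets to hemoglobin, hematocrit, a plasma protein or weight change. Section 9 compares interdialytic weight gain, which is not a correction.

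**The concern.** Between the two samples, water leaves the plasma. A substance or cell that stays in the blood is then more concentrated at 5 h even if its amount has not changed. One entry route selects patients for large weight gains, so the volume removed is not trivial.

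The stated secondary result is the change within each session, and nothing cancels there. An apparent rise in a marker could be reported as an inflammatory response to dialysis when it is only fluid removal. A real fall in a marker, or a modest loss of white cells or platelets, could be reported as no change. The second matters because the device works by binding leukocytes, and the Background describes its safety record partly by the absence of a fall in cell counts.

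**Working it through.** **The plan's own figure.** None is given for the marker or count analyses. The only calculation is the sample size of 10 for regional wall abnormalities (Section 9: difference 20%, SD 14%, alpha 0.05, power 80%). It reproduces: a two-sided paired t test with SD of differences 14 × √2 = 19.8 needs n = 10 (power 81.1%). This point does not touch it.

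**Size of the artefact from blood volume.** Assumptions, not in the documents: baseline hematocrit 0.33; blood volume falls by a fraction f; marker confined to plasma; no clearance, binding, bleeding or transfusion.

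- Plasma volume ratio = (1 − f − 0.33) / (1 − 0.33); marker rise = 1/ratio − 1.
- Cell-count rise = 1/(1 − f) − 1.

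| f | Plasma ratio | Marker rise | Cell-count rise |
|---|---|---|---|
| 5% | 0.62/0.67 = 0.925 | 8% | 5% |
| 10% | 0.57/0.67 = 0.851 | 17.5% | 11% |
| 15% | 0.52/0.67 = 0.776 | 28.8% | 18% |
| 20% | 0.47/0.67 = 0.701 | 43% | 25% |

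**A second route, from fluid removed.** Section 5.1.8 gives a weight gain above 0.04 kg/kg. Assume an extracellular volume at dry weight of 0.15-0.25 L/kg, with plasma contracting in proportion. Rise = fluid removed / extracellular volume.

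- At 0.04 kg/kg: 0.04/0.25 to 0.04/0.15 = 16% to 27%.
- At the ultrafiltration rate cited in the Background: 12.37 mL/h/kg × 4 h = 49.5 mL/kg, giving 20% to 33%.
- At 0.02 kg/kg (possible, because the hypotension entry route sets no minimum gain): 8% to 13%.

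The two routes give the same order of size.

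**Effect on the planned test.** Two-sided paired t test on the log change, n = 10, true change zero, nominal 5%. The SD of the log change is assumed.

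| Artefact | SD 0.2 | SD 0.3 | SD 0.5 |
|---|---|---|---|
| 10% | 27% | 15% | 8% |
| 17.5% | 62% | 33% | 15% |
| 20% | 73% | 40% | 18% |

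**Could a fall in cells be hidden?** The Background reports an average of 1.13 × 10⁹ cells bound to the device after 4 h. Assuming 4-6 L of blood and 4-8 × 10⁹ white cells/L, the circulating pool is 16-48 × 10⁹, so the bound cells are 1.13/48 to 1.13/16 = 2-7% of it. That is smaller than the 11-18% spurious rise.

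**Between sessions.** With equal net ultrafiltration the bias is zero. At an assumed 0.20 L/kg, 0.04 kg/kg removed in the heparin session against 0.03 in the device session gives 1.15/1.20 − 1 = −4%; against 0.02 it gives 1.10/1.20 − 1 = −8%.

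**Check of the correction.** At f = 10%, Hb0/Hbt = 0.9 and hematocrit becomes 0.33/0.9 = 0.367. The marker factor is 0.9 × (1 − 0.367)/(1 − 0.33) = 0.9 × 0.945 = 0.851, which equals the plasma ratio above.

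**The case against.** The strongest reply is that the device comparison is protected by design. Each patient is their own control. Both sessions last 5 h with the same flows, the same ultrafiltration-free first hour and the same dry-weight target, one week apart on the routine treatment day. This largely stands. A reader might infer that the comparison of the heparin and device sessions is itself materially biased; the documents give no reason to expect a large difference in net ultrafiltration. Equal removal is not guaranteed, since ultrafiltration is set from each day's weight, but the residual is small unless removal differs a good deal. The reply does not reach the within-session change, which is what the Synopsis names.

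The direction is also uncertain for some items. The dialyzer is high-flux, the device binds leukocytes, and no clearance or distribution volume is given for any marker. This stands: the artefact can produce an apparent rise, but need not. A rise in IL-10 would not be read as pro-inflammatory in any case.

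The correction can also err. It treats each marker as confined to plasma; for one that distributes more widely it may over-correct and create a false fall, which would favour the device. This stands, and is why corrected values should accompany the raw ones rather than replace them.

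Finally, these are secondary analyses of exploratory measurements in a 10-patient pilot. That limits the importance, but not the case for an adjustment that needs no new data.

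**Conclusion.** The point holds for what the plan says it will report: raw within-session change in marker concentrations, and the same change in white cells and platelets. Under the assumed hematocrit of 33% and a 10-15% blood-volume fall, the spurious rise is about 18-29% for plasma-confined markers and 11-18% for counts. None of these inputs is in the documents, and clearance, binding or sequestration could reduce or reverse the net change. Raw values cannot separate these effects.

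Three wider readings are not supported. Ultrafiltration will not necessarily make every marker rise. Flow-cytometry percentages, fluorescence intensity and wall motion are not concentrations and are not affected. The count criteria in step 8.3.1.43, before the device session, are absolute thresholds on measured values, and this point does not call them into question.

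**What to change.** Pre-specify in Sections 8.4.2 and 9 that, for both sessions, the 5 h changes in soluble markers, white cells and platelets are reported raw and corrected side by side:

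- soluble markers: measured value × (Hb0/Hbt) × (1 − Hctt)/(1 − Hct0);
- white cell and platelet counts: measured value × Hb0/Hbt.

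Here 0 is baseline and t is 5 h. Take hemoglobin and hematocrit from the blood counts already scheduled at both times (steps 8.3.1.12 and 8.3.1.28). The online hematocrit device is tied to the citrate protocol and is not stated for the heparin session, and albumin is scheduled only at baseline, so neither serves as well.

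Report net ultrafiltration for each session. Do not interpret a within-session change as inflammatory, or a count as not having declined, unless raw and corrected results agree.

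Apply the correction at 24 h only if a blood count is drawn then. Appendix 1 shows one, and the Appendix 2 volume fits it (18 mL / 3 mL = six draws, three per session), but steps 8.3.1.40 to 8.3.1.42 omit it; these should be reconciled.

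The cost is a little programming and no extra samples. The marker formula assumes confinement to plasma and no transfusion or bleeding between samples, and this should be stated beside the results. Safety thresholds on measured counts stay as they are.
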